12.7.1 Adverse Events

Adverse events (AEs) will be coded using MedDRA 24.0 or higher according to the version in use at time of database lock. All safety analyses of AEs will be performed by actual treatment arm and reported using the Safety Analysis Set. An AE will be considered a TEAE if it first occurs or worsens in severity or seriousness after the first dose of IMP intake and before the last dose date + 15 days.

All AEs will be classified during the pre-treatment period, the 51-day safety on-treatment period or during the follow-up period as follows:

Events that occurred before first IMP intake without worsening or becoming serious after the first IMP dose are classified as **pre-treatment AEs**;

Events that occurred or worsens between first IMP dose and 14 days after IMP last dose are classified as on-treatment AE and are defined as **treatment-emergent AEs** (TEAEs);

- TEAE occurring during 21-day on-treatment safety Period 1 will be considered emergent to actual treatment received during Period 1 (as defined in [Section 10.1.1](#)).
- TEAE occurring during 21-day on-treatment safety Period 2 will be considered emergent to actual treatment received during Period 2 (as defined in [Section 10.1.1](#)).

Events occurring more than 15 days after last dose are classified as **follow-up AEs**.

Consequently, TEAEs will be summarized by treatment arm using the actual treatment received at each given period. Any adverse event occurring during the wash-out period will be linked to the actual treatment arm defined for Period 1, whereas any AEs occurring after last IMP dose will be linked to the actual arm defined at time of permanent study drug discontinuation.

The following events will not be identified as AEs in this study:

- Medical or surgical procedures (e.g., surgery, endoscopy, tooth extraction, etc.). The condition (the “triggering event”) that leads to the procedure are adverse events and will be reported as such.

- Pre-existing conditions present or detected prior to the first dose of study drug that do not worsen during the study.

Counting rules

For incidence reporting, if a patient reported more than one AE that was coded to the same preferred term/system organ class within a given treatment arm, the patient will be counted only once for that specific preferred term/system organ class by treatment arm and the rules defined below will be applied.

For TEAEs presented by action taken on study drug, the worst action taken among the events with same SOC/PT emergent to the same treatment arm will be selected for each patient. If action taken is missing for a TEAE, the action taken “drug withdrawn” will be assigned considering the AE leads to permanent IMP discontinuation. The imputed values for action taken will be used for incidence summaries, while the actual values will be used in data listings.

For TEAEs presented by severity, the worst severity among the events with same SOC/PT emergent to the same treatment arm will be selected for each patient. If the severity is missing for a TEAE, then a severity of “Severe” will be assigned. The imputed values for severity assessment will be used for incidence summaries, while the actual values will be used in data listings.

For TEAEs presented by relationship to study drug, the relationship to study drug, as assigned by the investigator, for each event during the clinical trial will be presented for each patient. If the relationship to investigational product is missing for a TEAE, a causality of “Related” will be assigned. The imputed values for relationship assessment will be used for incidence summaries, while the actual values will be presented in data listings.

For TEAEs presented by categories for time of first onset of AE, if the AE start date is missing, it will be imputed as specified in [Table 10.14-1](#) for AE analysis or summary but actual values will be presented in data listing.

Summary of Adverse Events

For the purpose of inclusion in TEAE tables, incomplete AE onset and end dates will be imputed as specified in [Table 10.14-1](#) No duration will be calculated for adverse events with incomplete start-or stop dates, or for ongoing adverse events.

For summary by SOC and PT the denominator to derive the percentage will be the number of patients at risk in the treatment arm.

For subgroup analysis by SOC and PT the denominator to calculate the percentage will be the number of patients at risk in the treatment arm and in the category of the analyzed subgroup.

For summary by SOC and PT and category of time to first onset of AE the denominator to derive the percentage will be the number of patients at risk in the treatment arm in each time interval category.

For summary by SOC and PT and category of duration of AE the denominator to derive the percentage will be the number of patients in the corresponding treatment arm having experienced a TEAE corresponding to the SOC or PT being summarized.

The number of patients at risk in the treatment arm is defined as the number of patients having taken at least 1 spray of respectively nabiximols or placebo in the actual treatment arm (as defined in [Section 9.3.1](#)) linked to either the 21-day safety period 1 or the 21-day safety period 2 (as defined in [Section 10.1.1](#)).

All summary by SOC and PT will be alphabetically for SOC and by descending frequency of nabiximols for PT within SOC.

Listing of Adverse Events

All AEs, SAEs, AEs leading to study drug discontinuation, AE with outcome of death; AE of special interest will be listed.

The listings will include Subject ID, actual treatment received, SOC, preferred term, investigator term, start and stop date of the AE, whether or not the AE was treatment emergent, duration, frequency, severity, relatedness, action taken, outcome, and seriousness of the AE. Imputed start or stop dates will not be displayed in listings of AEs. These listings will be sorted by treatment sequence, subject ID and onset of adverse events.

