## **12.5      Causality Assessment**

Causality assessment is required for all AEs and SAEs. Causality assessment must only be assigned by the investigator. All cases judged as having a reasonable suspected causal relationship to the IMP must be reported as such. The expression "*reasonable causal relationship*" is meant to convey in general that there are facts (evidence) or arguments to suggest a causal relationship.

The following question, which must be answered by the investigator for all AEs, is used to capture the reasonable causal relationship of an event to the IMP:

*"In your opinion, is there a plausible relationship to the IMP?"* The answer is either "yes" or "no."

Events that start before the first dose of IMP (pretreatment) should be considered as not causally related. Where a pretreatment event worsens in severity following the first dose of IMP, a new event record should be entered into the eCRF.

Considering the explanation given above, investigators are strongly encouraged to express their opinion on what the cause of an AE might be. For individual patients, the investigator is usually in the best position to assess the underlying suspected cause of an AE. For all AEs and especially SAEs, it is important that the investigator assess not only the possible role of the IMP but also other potential contributing factors. Factors for consideration of the underlying cause may include the following:

- Medical and disease history
- Lack of efficacy/worsening of treated condition
- Concomitant or previous treatment
- Withdrawal of IMP
- Protocol-related procedure

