**D)      Severity**

When describing the severity of an AE, the terms mild, moderate, or severe should be used. Clinical judgment should be used when determining which severity applies to any AE.

If the severity of an AE fluctuates day-to-day, e.g., a headache or constipation, the change in severity should not be recorded each time; instead, only the worst observed severity should be recorded with AE start and stop dates relating to the overall event duration, regardless of severity.

A severe AE is not the same as an SAE. For example, a patient may have severe vomiting, but the event does not result in any of the SAE criteria above. Therefore, it should not be classified as serious.

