10.0 Conventions and Derivations

10.1 Study Period, Reference Day, Study Day, Analysis Day and Visit Window

10.1.1 Study Periods

For each patient, there will be a screening period, an evaluable period composed of a treatment period 1, a washout period, and a treatment period 2, and a safety follow-up period.

The Screening period starts on the day of the informed consent signature and ends on Day 1 (as defined on in [Section 10.1.2](#)) before 1st IMP intake.

The evaluable period starts on the day of randomization and ends the day of the safety follow-up visit.

- The **51-day efficacy period** which starts on the first day of IMP administration and ends at the end of treatment date.
 - This period will be composed of:
 - The **21-day on-treatment efficacy Period 1** which starts the day of first IMP intake during Period 1 and ends the earliest between end of Period 1 Day 21 date and permanent end of treatment date;
 - The on-treatment **wash-out period** which begins the day following the end of the 21-day on-treatment efficacy Period 1 and ends the day before the beginning of the 21-day on-treatment efficacy Period 2;
 - The **21-days on-treatment efficacy Period 2** which starts the day of IRT call for Period 2 and ends on the end of treatment date. This period is only defined for patients exposed to IMP during Period 2.
 - It will be used for efficacy analyses using the Full Analysis Set.
- The **51-day safety period** which starts on the first day of IMP administration and ends at the end of treatment date (+ x days).
 - This period will be composed of:
 - The **21 day on-treatment Safety Period 1** which starts the day of first IMP intake during Period 1 and ends the earliest between end of the wash out period date, the day before the date of IRT call for Period 2, the day before Visit 6 date and permanent end of treatment date + x days.
 - The **21 day on-treatment Safety Period 2** which starts the earliest between date of Visit 6, day of IRT on treatment safety period call for Period 2 date, and ends on the end of treatment day date + x days.
 - x will be equal to 14 days for Adverse events, 4 days for C-SSRS and 0 days otherwise.
 - it will be used for safety analyses using the Safety Analysis Set (unless otherwise specified).
- The **Follow-up period** which starts the day following the 51-day on-treatment safety period and ends on the end of study date.

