10.21 Adverse Events

10.21.1 Start and Stop Date Imputation

Table 10.21-1 Imputation Rules for Partial Adverse Events Start/Stop Dates

Parameter	Missing	Additional Conditions	Imputation
Start date for AEs	D	M and Y same as M and Y of first dose of study drug	Date of first dose of study drug
		M and/or Y not same as date of first dose of study drug	First day of month but should fall after 1st study drug intake or if impossible after informed consent date
	D and M	Y same as Y of first dose of study drug intake during period 1 and 2	Date of first dose of study drug
		Y after Y of first dose of study intake during Period 1 but same Y as 1 st study drug intake during Period 2	Date of first drug intake during period 2
		Y prior to Y of first dose of study drug but same as Y of informed consent date	Date of informed consent
		Y after Y of last study drug intake	The earliest date between date of last study drug intake + 14 days and end of study date
	D, M, Y	Not allowed by the system	Not applicable
Stop date for AEs	D	M and Y same as M and Y of last dose of study drug	The earliest date between date of last dose of study drug and end of study date
		M and/or Y not same as date of last dose of study drug	The earliest date between last day of month and end of study date
	D and M	Not allowed by the system	Not applicable
	D, M, Y	Not allowed by the system	Not applicable

AE = Adverse events; D = day; M = month; Y = year

Note: In all cases, if an estimated start date is after a complete stop date, use the first day of the stop date month. Similarly, if the estimated stop date is before a complete or imputed start date, use the last day of the start day month.

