10.21.3 Time to First Onset of AE

The time to first onset of AE will be defined by study period as:

- AE start date – IMP start date in the studied period

For AEs with an onset date occurring during the 21-days on-treatment safety Period 1 (as defined in [Section 10.1.1](#)) the IMP start date refers to the date of 1st IMP spray intake during Period 1.

For AEs with onset date occurring during the 21-days on-treatment safety Period 2 (as defined in [Section 10.1.1](#)), the IMP start date refers to Period 2 start date provided that the patient is exposed during Period 2.

Based on the above value time to first onset of AE will be categorized as:

- 1-7 days,
- 8 to 14 days,
- 15 to 21 days,
- >21 days.

If onset time is shorter as 1 day, it will be included in the 1-7 days category.

For the purpose of time-to-event analysis, censoring rules are defined in [Section 12.7.2.3](#).

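### Safety rules not tied to the treatment period: early stoppers' scheduled labs are handled inconsistently, month-only AE dates default to Period 1, and worsening in Period 2 has no stated attribution

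*SAP*

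**What the plan says.** **Lab and ECG window.** SAP 10.1.1 ends each on-treatment safety period no later than permanent end of treatment plus x days: "x will be equal to 14 days for Adverse events, 4 days for C-SSRS and 0 days otherwise". Labs and ECG are scheduled after baseline only at Visits 5 and 9. Patients who stop IMP are encouraged to stay to the end of that period (Protocol 4.1).

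**Partial AE dates.** In SAP Table 10.21-1 a start date without a day becomes the first dose of the trial if it lies in that month. Otherwise it becomes: "First day of month but should fall after 1st study drug intake or if impossible after informed consent date". A year-only date becomes the first dose of the trial when both periods start in that year, and the Period 2 first dose when Period 2 starts in the next year. SAP 12.7.1 cites Table 10.14-1, the medication table, for this imputation; its relevant start-date rules are essentially the same.

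**Worsening and attribution.** Besides "An AE will be considered a TEAE if it first occurs or worsens in severity or seriousness after the first dose of IMP intake", SAP 12.7.1 says "TEAE occurring during 21-day on-treatment safety Period 1 will be considered emergent to actual treatment received during Period 1" and uses the same wording for Period 2. SAP 10.21.3 works from onset date: "For AEs with an onset date occurring during the 21-days on-treatment safety Period 1". Protocol 12.6 D says that when severity fluctuates from day to day, "only the worst observed severity should be recorded with AE start and stop dates relating to the overall event duration, regardless of severity". Protocol 12.5 asks for a new record in one case: "Where a pretreatment event worsens in severity following the first dose of IMP, a new event record should be entered into the eCRF".

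**Still in force.** Table 3.2-1 of the SAP addendum keeps TEAEs, labs and ECG as set out in the SAP after early termination.

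**The concern.** In a crossover, each safety finding has to be assigned to the drug taken when it arose. These rules were written around the first dose of the trial and the last dose of IMP, not around each period. Three results could go wrong:

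- Patients who stopped early, a group of particular safety interest, can be missing from on-treatment lab outputs.
- Period 2 events with incomplete dates can be counted under the other treatment.
- A mild Period 1 event that becomes severe, or leads to withdrawal, in Period 2 can carry its worst severity and action taken into the Period 1 arm, because the severity and action tables take the worst event emergent to each arm.

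At stake is the by-arm safety comparison, which is one of the few parts of the SAP that the addendum leaves in full.

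**Working it through.** The documents give no figure to reproduce here, so the check traces the rules and enumerates the date rule.

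**1. Lab lag.** Days off drug at the scheduled sample = 21 − day of last dose in the period. The visit window is Day 19 to 23.

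| Last dose | Day 21 sample, days off drug | Over the visit window |
|---|---|---|
| Day 3 | 18 | 16–20 |
| Day 7 | 14 | 12–16 |
| Day 10 | 11 | 9–13 |
| Day 14 | 7 | 5–9 |
| Day 18 | 3 | 1–5 |

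Every value exceeds x = 0. The outputs then divide as follows:

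- *Excluded:* the out-of-range summary and the last-on-treatment scatterplot (12.7.3) and the DISH plot (12.7.3.1), all limited to on-treatment values.
- *Included:* the liver-injury table (12.7.3.1), which takes any post-baseline visit and links values after discontinuation to the last treatment.
- *Unclear:* Day 21 change and shift tables and ECG tables. Section 10.1.3 only prefers on-treatment values, and Table 10.1-2 runs the lab and ECG window to the last visit of the period. Section 12.7 limits safety analyses to the on-treatment period, and 12.7.3 uses the latest on-treatment lab value.

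**2. Partial dates.** Assumptions: Day 1 equally likely on each of the 730 dates in 2021–2022, Period 2 first dose on Day 31, onset equally likely on each day of the window. The month-only rule was applied and imputed dates before the Period 2 first dose were counted.

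| True onset | Cases | Imputed before Period 2 |
|---|---|---|
| Days 31–51 | 730 × 21 = 15,330 | 9,786 (64%) |
| Days 31–58 | 730 × 28 = 20,440 | 10,696 (52%) |
| Days 31–65 (Day 51 + 14) | 730 × 35 = 25,550 | 10,746 (42%) |
| Days 1–30 | 730 × 30 = 21,900 | 21,900 (none moves into Period 2) |

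Example: with Day 1 on 10 March, Period 2 starts on 9 April. An AE dated April becomes 1 April, which is Day 23, in washout, and counts to Period 1. Counter-example: with Day 1 on 1 March, Period 2 starts on 31 March, and an AE dated April becomes Day 32 and counts to Period 2.

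Of year-only onsets on Days 31–51, 89% go to Period 1 (87% for Days 31–65). The rest fall under the next-year rule or, around New Year, under no rule.

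**3. Worsening.** No arithmetic applies. TEAE status looks back to one dose. Attribution follows the period in which the TEAE is occurring, without saying whether worsening counts as occurring. The one section that names a date for placing an AE in a period uses onset. A single record with worst severity and overall start date would therefore probably be placed in Period 1.

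**The case against.** The strongest reply is that the effects are small, partly unwritten and balanced.

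- **Worsening.** No sentence sends a Period 2 worsening to Period 1. The onset-date wording belongs to the time-to-onset derivation. The single-record rule concerns day-to-day fluctuation, and Protocol 12.1.1 counts worsening of a preexisting condition as an AE, which could support a new record. This stands: the defect is a missing rule, not a written misattribution.
- **Partial dates.** Protocol 12.6 B says they are not normally acceptable and asks for an estimated date. This stands: the percentages apply only to events dated by month alone, and the documents give no count of these.
- **Labs.** The liver-injury table keeps off-drug values, and the Day 21 tables may. Period 2 stoppers normally have a Visit 5 sample, and one version of the out-of-range summary admits unscheduled visits. This also stands, but it leaves the on-treatment-only outputs and the contradiction between sections untouched.

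A reader might infer that the rules hide nabiximols harm under placebo. The documents do not support that. Allocation is 1:1, and in the nabiximols/placebo sequence the same rules move placebo events to nabiximols. A reader might also infer that early stoppers' labs and ECGs vanish from all safety tables; only the three outputs listed as excluded clearly lose scheduled lab samples.

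**Conclusion.** The point holds in a limited form. The lab rule and the month-only rule give wrong results if followed exactly, and the worsening rule is incomplete. The lab exclusion follows from x = 0 and the visit schedule and needs no assumption. The 42% to 64% range rests on evenly spread first doses and onsets, on Period 2 starting at Day 31, and on the length of the onset window; it is a share of month-only Period 2 events, not of all AEs. The error is one-directional by period but runs both ways by treatment, so it blurs the contrast between arms. Numbers of events are probably small, and smaller again because enrollment was halted before the planned number was reached. The change is still worth making, because safety reporting is retained and the SAP can be corrected before unblinding.

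**What to change.** Change the SAP only, before unblinding.

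1. **Labs and ECG.** Extend the on-treatment safety window to the last visit of the period in which IMP was stopped (before Visit 6 for Period 1). Attribute those values to that period's treatment, flag them as off drug, and apply this to the out-of-range summary and the DISH plot. Setting x = 14 would not be enough: 21 − 14 = 7, so a last dose before Day 7 still puts a Day 21 sample outside.
2. **Partial dates.** Add a treatment-neutral, period-aware rule. For example, impute the Period 2 first-dose date when the partial month is that of the Period 2 first dose and not that of the Period 1 first dose, unless other data place the onset earlier. Cite Table 10.21-1 in 12.7.1. The last condition is essential. In the enumeration above, the example rule without it cuts misplaced Days 31–51 onsets from 9,786 to 14 of 15,330, but moves 10,326 of 21,900 (47%) month-only onsets on Days 1–30 into Period 2. The stop date, and the visit at which the AE was first reported if that is recorded, should be used to settle these cases.
3. **Worsening.** Define emergence and worsening relative to the first dose of each period, and attribute events leading to discontinuation to the period in which IMP was withdrawn. Where a single record does not date the worsening, the rule cannot be applied; list such AEs if ongoing at the Period 2 first dose.

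The cost is SAP wording and programming. Some lab values will be from days to two weeks or more off drug, and some month-only Period 1 or washout events may move to Period 2. A new instruction to sites on AE records would be largely moot now that enrollment has stopped.

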## **12.6 Reporting Procedures for All Adverse Events**

All AEs (including SAEs) occurring during the trial will be reported on the running logs in the AE section of the eCRF. This includes all events from the time following Screening (Visit 1) up to and including the Safety Follow-up Visit (Visit 10), whether or not attributed to IMP and observed by the investigator or patient.

The following information will need to be provided for all AEs:

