**F)      Action Taken With Trial Medication**

This question refers to the action taken with the IMP due to an AE. The action with the IMP must be classed as follows:

- Dose Not Changed
- Dose Reduced
- Drug Interrupted
- Drug Withdrawn

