7.0 Statistical Methods

The abbreviated reporting will follow the strategy as detailed in **Table 3.2-1**.

Table 3.2-1 Strategy for abbreviated reporting

Hierarchy	GWSP20105	
Primary	LLMT-6	Inferential and descriptive statistics; no supplementary, no subgroup analyses and no imputations for missing data
Secondary	LLMT-4	As established in study SAP to support safety assessment of Nabiximols as a globally marketed product
	TEAEs	
	Vital signs	
	Labs	
	ECG	
	C-SSRS	
Exploratory	PK	No processing, analyses, or reporting
	T25FW	Data cleaning for inclusion in listings; no descriptive or inferential statistics
	NRS spasticity	
	Daily spasm count	
	MSSS-88	

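### A blank action taken on an adverse event is imputed as 'drug withdrawn' with no check against the End of Treatment record, so a patient known to have continued IMP could be tabulated as a permanent discontinuation

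*SAP*

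**What the plan says.** **The rule.** Among the counting rules of SAP 12.7.1, a TEAE with no recorded action taken is given the value 'drug withdrawn', which "will be assigned considering the AE leads to permanent IMP discontinuation". The next sentence says where this applies: "The imputed values for action taken will be used for incidence summaries, while the actual values will be used in data listings".

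**What sites must record.** Protocol 12.6 introduces its list of items with "The following information will need to be provided for all AEs". Item F is the action taken: "The action with the IMP must be classed as follows". Four answers follow: dose not changed, dose reduced, drug interrupted and drug withdrawn. The list has no 'not applicable'.

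**Which events count as TEAEs.** SAP 12.7.1 states: "Events that occurred or worsens between first IMP dose and 14 days after IMP last dose are classified as on-treatment AE". It adds: "Any adverse event occurring during the wash-out period will be linked to the actual treatment arm defined for Period 1". Some TEAEs therefore begin when the patient is taking no IMP.

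**What else records stopping.** SAP 10.6 and 10.7 take the end-of-treatment dates from separate End of Treatment forms for Period 1 and Period 2. SAP 12.1 tabulates early discontinuation of study drug with its reason.

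**Current reporting.** After the early termination, Section 7.0 of the SAP addendum keeps the safety outputs: "As established in study SAP to support safety assessment of Nabiximols as a globally marketed product". The table layout is damaged, but this text appears to belong to the TEAE and other safety rows.

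**The concern.** Severity and causality are judgements with no second source, so a worst-case value for a blank is a defensible convention. Whether a patient permanently stopped IMP is a recorded fact. The rule fills a blank with a statement about that fact and does not ask what the other forms say.

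TEAEs leading to permanent IMP discontinuation are a main tolerability result. They appear in the overall summary (SAP 12.7.1.1), the SOC and PT tables and their subgroups (12.7.1.2), the serious TEAE tables (12.7.2.2) and the AESI summaries (12.7.2.3). If imputed cases enter these counts, the tables may show more discontinuations than disposition does. SAP 12.7.1 also sets a blank relationship to 'Related'. A record with both fields blank could then count as a treatment-related discontinuation.

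**Working it through.** The plan states no discontinuation rate, AE rate or rate of blanks, so there is no figure to reproduce. The check is to follow three hypothetical patients, each with one TEAE and a blank action taken, through the rules.

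| Patient | End of Treatment and disposition record | Value under SAP 12.7.1 | Listing |
|---|---|---|---|
| A: event on Day 25 (washout), doses on Day 31, completes | No early discontinuation | Drug withdrawn, Period 1 arm | Blank |
| B: last dose on Day 51, event on Day 54 | Completed treatment | Drug withdrawn, Period 2 arm | Blank |
| C: event on Day 25 that prevents entry to Period 2 | Stopped early because of an AE | Drug withdrawn, Period 1 arm | Blank |

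- **A and B.** The imputed value contradicts the record. A also conflicts with the estimand text in SAP Table 9.1-2, under which patients who discontinue IMP in Period 1 have no Period 2 data collected. A does have Period 2 data.
- **C.** The imputed value is right. A repair must not lose this case.

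**Against the protocol.** Protocol 13.6.6.2 asks for a summary of TEAEs reported as the cause of permanent cessation. An imputed blank was not reported as such. SAP Table 6.2-1, which lists changes from the protocol, does not mention this one.

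**How far the rule reaches.** Its opening words concern TEAEs presented by action taken, which matches one table in SAP 12.7.1.2. The clause on permanent discontinuation and the term 'incidence summaries' point to the discontinuation tables as well. The text allows both readings.

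**Time off drug.** The inputs are two 21-day treatment periods, the washout of Days 22 to 30 (9 days, Protocol 9.1.3) and 7 to 10 days from last dose to Visit 10 (Protocol 9.1.5).

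- Shortest follow-up: (9 + 7) / (42 + 16) = 16/58 = 27.6%
- Longest follow-up: (9 + 10) / (42 + 19) = 19/61 = 31.1%

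These are shares of calendar days. They show that patients like A and B can arise, but not how often.

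**Weight of one miscounted patient.** The denominator in SAP 12.7.1 is the number of patients who took at least one spray of that treatment. The actual number is not given, and enrolment stopped before the planned number was reached (addendum 6.0). Assumed values:

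- 1/190 = 0.53 percentage points (planned randomised total)
- 1/170 = 0.59 percentage points (planned completers)
- 1/85 = 1.18 percentage points (half the planned completers)

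**The case against.** The strongest reply is that the rule may rarely operate. Action taken is required for every AE (Protocol 12.6), and Protocol 16.3 provides for checks on omissions and queries to sites. The imputation is then a fallback for what is still blank. It is pre-specified, applies equally to both arms and matches the worst-case rules for severity and causality. Because the listings keep actual values, imputed cases can be traced. All of this stands, and it limits the point to what could happen if blanks remain.

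A reader might infer from the four-answer list that the form offers no valid entry for an event that starts off drug, and that blanks are therefore to be expected. The documents do not support this. The eCRF is not among them, and the list is the protocol's. Item F asks what was done with IMP because of the event. 'Dose not changed' can be a literal answer for an off-drug event without consequence, and 'drug withdrawn' can be true of a washout event that ends treatment.

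The narrow reading of the rule also has force. If it governs only the action-taken table, the discontinuation tables are unaffected. That does not remove the point: the action-taken table could still contradict the record, and the SAP should state which reading is meant.

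**Conclusion.** The point holds as a minor one. The SAP contains an unconditional imputation that can override recorded data on whether a patient stopped IMP. A false count requires that a blank remains after querying and that the patient did not in fact stop because of an AE. For it to reach the discontinuation tables, the wider reading must also apply.

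No inflation can be quantified, because the number of blanks is unknown. A reader might take the 28% to 31% of days off drug as a measure of the error. It is not a share of events, patients or blanks. Nor do the documents show a bias towards either arm: a blank in a placebo period would raise the placebo count in the same way.

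**What to change.** Amend SAP 12.7.1, or the addendum, before unblinding:

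1. Count a TEAE as leading to permanent IMP discontinuation only if it is reported as such, or if action taken is blank and the End of Treatment or disposition record shows that the patient permanently stopped IMP early because of an AE. Include a washout AE that prevented entry to Period 2.
2. Show every other blank as 'missing/not applicable' in the action-taken table.
3. Reconcile the discontinuation tables with disposition, by period.
4. State that the same definition applies to all tables in SAP 12.7.1.1, 12.7.1.2, 12.7.2.2 and 12.7.2.3.

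The condition should rest on the recorded reason and not on whether the last dose falls after the AE onset. Patient C's last dose is on Day 21 and the event on Day 25, so a date test would miss a true AE discontinuation. Adding a 'not applicable' option to the eCRF would help little now that enrolment has stopped.

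The cost is a few sentences, minor programming and one extra row in the action-taken table.
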